STUDY PROTOCOL
May 1, 2017

Project Title: Integrating Safer Conception Counseling to Transform HIV Family Planning Services

NCT03167879

Registered on clinicaltrials.gov on 5/23/17

STUDY PROTOCOL

Overview. This 3-arm, cluster RCT will compare two models for implementing a comprehensive FP program that integrates SCC within current FP services in HIV clinics—an up to 6-session, multi-component, structured SCC intervention (SCC1), and a workshop to train FP providers on use of SCC guidelines (SCC2)—versus existing FP services (usual care). Both SCC1 and SCC2 will use routine screening for fertility desires and a workshop for training FP nurses to implement SCC, but SCC1 is differentiated by its use of a structured counseling SCC protocol and manual (as opposed to the clinical acumen of the trained FP nurses), and inclusion of client outreach and ongoing supervision support. Each arm will be implemented at 2 sites (6 sites in total) and each site will enroll 65 clients (total n=390) with serodiscordant partners who have childbearing desires at recruitment. Participants will be surveyed at baseline, months 6 and 12, and post-pregnancy for those who become pregnant prior to month 12. The primary outcome is correct use of SCM or contraception (depending on desired pregnancy status following SCC consult); secondary outcomes are pregnancy status, PMTCT use (if pregnant), partner seroconversion, and condom use. A cost-effectiveness analysis will also compare the 3 arms to inform policy and practice recommendations for settings of various resource levels.

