Study Setting. The study will be conducted at 6 HIV clinics operated by The AIDS Support Organization (TASO), which are located in Masaka, Entebbe, Mbarara, Jinja, Mbale, and Rokangira. These sites are *highly comparable with regard to size of clientele, provider composition, and makeup of FP services, and are close enough to Kampala for facilitating effective coordination and oversight of the research*. TASO partnered with us to plan the proposed models for integrating SCC into its FP services, and to pilot SCC1 (see D.1). Each site resides within a hospital campus, provides HIV care to 6000-8000 index clients (65-75% female, 75-80% aged 15-49, ~70-80% on ART), with a staff of 15-20 medical providers (incl. 3-4 FP nurses), 12-15 counselors and 6-10 expert clients. Each provides reproductive health and FP services in-house, which focus on contraception and PMTCT; contraceptives provided onsite include oral pills, injectables, and condoms, while implants and tubal ligation require referral to nearby FP clinics. Other related services at TASO include assisted disclosure (including home-based couples HIV testing), and male circumcision.

Cluster RCT of two models for integrating SCC within existing FP programs vs. usual care

[figure not shown]
Each site will be randomly assigned (a blind drawing witnessed by the leadership of each clinic) to use one of the two models for integrating SCC into FP services (SCC1 or SCC2), or usual care (existing FP services).

Arm 1: Multi-component, structured intervention for integrating SCC into FP (SCC1)

Drawing on an ecological adaptation of the Information, Motivation and Behavioral skills (eIMB) model of behavior change,⁵⁷ we developed a multi-component intervention that identifies and engages HIV clients (and partners) with fertility desires into SCC to facilitate an informed decision process regarding childbearing and corresponding use of contraception or SCM (and PMTCT once pregnant) based on their desired pregnancy decision. Applied to this context,

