Power analysis: 11% of PLHA in Uganda who want to prevent pregnancy use dual contraception³⁰ and our research shows 15% of PLHA trying to conceive use TUI or MSI.³⁷ Therefore, we expect the usual care arm will have a 15% rate of correct use of contraception/SCM (depending on pregnancy intentions), which is the primary outcome. Using an intra-class correlation (ICC) of 0.01 to control for clustering, based on other studies of reproductive health outcomes,⁷⁴ and 10% attrition at Month 12 (given the 6% in our current study), we will have > 80% power (2-tailed test) to detect a 4.5 percentage point difference (small effect size; $d=.15$) for our comparison of the usual care arm to the combined SCC1 & SCC2 arms on the use of contraception or SCM at month 12, and a 7-8 percentage point difference between the SCC1 and SCC2 intervention arms. In analysis of effects on contraception and SCM use separately, and with half the sample expected to decide to pursue pregnancy and half contraception based on our pilot data, our sample size will provide > 80% power to detect a 6.5 percentage point difference with regards to each of the outcomes when comparing usual care to SCC1 and SCC2 combined, and 8-9 percentage point difference between the SCC1 and SCC2 interventions.

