Data analysis: Our primary analysis will be to compare the combined intervention arms (SCC1 & SCC2) against the usual care control to assess the effects of integrating SCC into FP services, and then compare the outcomes between the two intervention arms to determine whether the more intensive SCC1 shows a larger effect than the less intensive SCC2. The primary outcome-- correct use of contraception/SCM (depending on pregnancy intention)-- will be represented as a binary variable as defined in D.2.3.5, but we will also explore a categorical or continuous outcome derived from frequency of correct use throughout the study. Secondary outcomes to be investigated are pregnancy status, PMTCT use, consistent condom use, and seroconversion of partner. We will use an intent-to-treat approach in the primary analyses; secondary analyses will use only study completers. Participants remain in the study and analysis regardless if their relationship status changes during the study. Attrition weights will be used to account for dropouts, and analyses will incorporate design effects from this weighting in the calculation of standard errors and tests of significance. We will account for clustering, and with only 9 clusters/clinics we will conduct individual level analysis. Regression methods can directly model correlations among units in a cluster (random effects or multilevel models) or more simply adjust standard errors for clustering (GEE, robust standard errors), but these approaches are not reliable with so few

clusters,⁷⁵ so we'll use standard regression methods, but rather than attempt to estimate ICC directly, we will explore the sensitivity of significance levels using a range of plausible ICCs values for the outcomes.

Aim 1: Assess intervention effect on contraception/SCM use: *Hypothesis: Both SCC1 and SCC2 will be superior to usual care, and SCC1 will be superior to SCC2 regarding the primary outcomes.* We'll use logistic regression to compare rates of contraception or SCM use (depending on pregnancy intention) in the SCC1 and SCC2 interventions compared to the control condition, and investigate differences between SCC1 and SCC2 in a separate regression. The models will include covariates to adjust for baseline variables (e.g., childbearing stigma, age, sex) that may differ at baseline and to increase precision of the estimates.

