Aim 2: Assess intervention effect on secondary outcomes (pregnancy status; PMTCT use, consistent condom use, partner seroconversion): We will use the same analytic strategy as described for Aim 1.

Aim 3: Examine eIMB moderators and mediators of intervention effects on SCM and contraception use. We will identify bivariate correlates of the primary outcome from among baseline variables using correlation coefficients, t-tests and chi square tests, followed by a stepwise regression approach to identify a parsimonious list of predictors. We will then use longitudinal analyses to investigate changes in the primary outcome relative to changes in dependent variables such as SCM knowledge, motivation and self-efficacy. Like the baseline cross-sectional analysis described above, we will start with bivariate analyses that will inform a subsequent stepwise regression approach. We will use clinic fixed effects, because with only 9 clinics, clustering standard errors to correct for correlation between patients in the same clinic would significantly reduce power. Robust estimation techniques can adjust for correlation in multiple observations of a given patient over time. We will use a similar analytic approach to examine determinants of the secondary outcomes. Lastly, we will investigate the paths through which the intervention works, and subgroups that benefit more from the intervention. E.g., male clients and their partners may use contraception/SCM more because of their greater control over decision making and ability to secure partner participation in SCC. We can test this hypothesis by adding an interaction term between gender and the intervention. Using methods described by MacKinnon⁷⁶ and others,^{77,78} we will assess whether the intervention has a direct impact on contraception/SCM use or mostly though a mediating variable such as communication with provider about childbearing needs (which may result in clients being more apt to receive the information and encouragement needed to use SCM/contraception).^{46,79}

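### Clinics are randomised, but no ICC is named for the headline p-value and CI; if the uncorrected logistic regression decides, type I error is about 12% at the plan's own ICC of 0.01

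*Combined protocol and SAP*

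**What the plan says.** The clinic is the unit of randomisation. The section describing the cluster RCT says "Each site will be randomly assigned (a blind drawing witnessed by the leadership of each clinic", and the Overview says "Each arm will be implemented at 2 sites (6 sites in total".

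The Data analysis section states an intent and a level of analysis: "We will account for clustering, and with only 9 clusters/clinics we will conduct individual level analysis". It sets aside random-effects models, GEE and robust standard errors as unreliable with so few clusters. It then chooses "standard regression methods, but rather than attempt to estimate ICC directly, we will explore the sensitivity of significance levels using a range of plausible ICCs". The range is not given. The only design effect that it writes into the standard errors and tests is the one from attrition weighting.

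Aim 1 names "logistic regression to compare rates of contraception or SCM use" for the comparison with usual care, and will "investigate differences between SCC1 and SCC2 in a separate regression". Neither model has a cluster term or a cluster variance. Aim 2 adds, for the secondary outcomes, "We will use the same analytic strategy as described for Aim 1".

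A numerical ICC appears only in the Power analysis: "Using an intra-class correlation (ICC) of 0.01 to control for clustering".

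**The concern.** Rejecting GEE and mixed models with so few clinics is defensible. The gap is in what replaces them. An exploration over an unstated range, with no deciding value, does not fix the p-value or interval that tests either hypothesis. The only test specified completely enough to run is the uncorrected logistic regression, which treats clients of one clinic as independent.

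Two analysts who both follow the text could therefore draw opposite conclusions from the same data, one at ICC 0 and the other at ICC 0.01. If the uncorrected result is the one reported, both primary contrasts are anti-conservative, and chance differences between a handful of clinics can pass for an effect of the counselling programme.

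**Working it through.** **Inputs**
- 6 clinics, 2 per arm, 65 clients each, N = 390 (Overview).
- 10% attrition, ICC 0.01, usual care rate 15%, two-tailed test (Power analysis).
- Assumed: alpha 0.05, which the documents do not state.
- Analysed per clinic: m = 65 × 0.9 = 58.5. The pooled contrast is 234 vs 117 clients (4 vs 2 clinics). SCC1 vs SCC2 is 117 vs 117 (2 vs 2 clinics).

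**The plan's own figure.** The documents give no type I error. Their stated power (above 80% for 15% vs 19.5%) does not reproduce: it is 12.0% at ICC 0.01 and 16.9% with no clustering. That is a separate problem, and nothing below depends on it.

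**Type I error of the uncorrected test**
- Design effect: DE = 1 + (m − 1) × ICC = 1 + 57.5 × 0.01 = 1.575, and √DE = 1.255.
- Type I error = 2 × [1 − Φ(1.96/√DE)] = 2 × [1 − Φ(1.562)] = 11.8%.
- With 66 clients per site (m = 59.4, DE 1.584) it is 11.9%. With 9 clinics sharing 390 clients (m = 39, DE 1.38) it is 9.5%.
- Beta-binomial simulation (200,000 trials, 6 clinics of 58, all rates 15%, ICC 0.01), pooled / SCC1 vs SCC2: Pearson test 11.6% / 11.8%; Wald test from logistic regression 11.0% / 11.2%.

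**Where the conclusion changes.** A corrected p of 0.05 needs an uncorrected p of 2 × [1 − Φ(1.96 × 1.255)] = 0.014. Every uncorrected p from 0.014 to 0.05 is therefore significant at ICC 0 and not at ICC 0.01. In observed differences (percentage points):

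| Contrast | Reference arm observed at | Pearson test | Logistic Wald test |
|---|---|---|---|
| Pooled SCC vs usual care | 15% | 9.0 to 11.7 | 9.1 to 11.9 |
| SCC1 vs SCC2 | 15% | 10.3 to 13.2 | 10.4 to 13.5 |
| SCC1 vs SCC2 | 30% (assumed) | 12.3 to 15.6 | 12.4 to 15.7 |

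**Effect of fixing the ICC at 0.01.** With standard errors multiplied by 1.255, type I error is 2 × [1 − Φ(1.96 × √(1.575/DE at the true ICC))]. All true ICCs other than 0.01 are assumed.

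| True ICC | Uncorrected | ICC fixed at 0.01 |
|---|---|---|
| 0 | 5.0% | 1.4% |
| 0.005 | 8.4% | 3.0% |
| 0.01 | 11.8% | 5.0% |
| 0.02 | 18.1% | 9.3% |
| 0.05 | 31.9% | 21.1% |

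In simulation at ICC 0.01 the fixed-ICC test gives 5.0% / 4.8% (Pearson) and 4.5% / 4.3% (Wald).

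**Secondary outcomes.** At ICC 0.01 with assumed rates and cluster sizes, the uncorrected Pearson test gives 5.3% to 8.4%. Examples are 7.8% / 5.3% for a 1% event rate with 58 per clinic, and 8.1% / 8.4% for a 50% rate with 29 per clinic. The 12% does not carry over, so no size is claimed for Aim 2.

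**Limits.** Covariates and attrition weights were not simulated.

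**The case against.** The strongest reply is that the plan does deal with clustering. It says so, gives a reason for rejecting three methods, and recalculates significance over plausible ICCs. Since the Power analysis uses 0.01, that value would naturally lie in the range. On this reading the gap is one missing multiplier, and 12% describes a decision that the plan never states.

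Part of this stands. The 12% is conditional on the uncorrected result deciding, and the outcome, contrasts and model are otherwise defined. But the missing multiplier decides significance across a realistic band of results, and the uncorrected p-value is the only one that can be computed from the text alone.

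A second reply is that fixing 0.01 is only a partial repair, because error is still 21% at a true ICC of 0.05, more than the 12% complained of. That compares different true ICCs. At 0.05 the uncorrected test gives 32%, and the fixed-ICC test has the lower error at every positive ICC checked. It is true that the documents do not show 0.01 to be right for this composite outcome. Deciding at the top of a stated range would also be a valid rule.

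Third, covariates and weights could move the thresholds, and baseline adjustment could lower the residual ICC. This stands as a limit on precision. The difference between the Pearson and Wald figures is trivial.

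**Conclusion.** The concern holds and should be corrected before analysis. Neither primary contrast has a defined headline p-value or interval, because no ICC is named to set them. If the uncorrected regression decides, type I error is about 12% against a nominal 5%. That figure rests on a true ICC of 0.01, a two-sided 5% level, six clinics and about 58 analysed per clinic. With nine clinics sharing 390 clients it is 9.5%, so the conclusion survives either clinic count. Whatever the true ICC, a result with an uncorrected p between 0.014 and 0.05 has no defined interpretation under the present text.

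**What to change.** - For both contrasts, make primary the CI and p-value with standard errors multiplied by √(1 + (m − 1) × 0.01), about 1.25 for six clinics, on top of the attrition-weight design effect.
- State the ICC range in advance (for example 0 to 0.05) and label it sensitivity. Show the uncorrected regression only as the ICC = 0 row.
- State that 5% is held only if the true ICC is about 0.01 or less (about 9% at 0.02 and 21% at 0.05).
- Optionally, add a clinic-level analysis on 3 degrees of freedom as a supportive check that needs no assumed ICC. State its much lower power and its 6–7% error for SCC1 vs SCC2 when arm rates are unequal.
- Reconcile the clinic count: 6 in the Overview and Study Setting, 9 in Data analysis and Aim 3, and 9 implied by the coordinator workload under Recruitment. Reconcile 65 clients per site (Overview) with 66 (Research Participants). The clinic count changes the multiplier from 1.255 to 1.175; 65 vs 66 barely matters.

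The cost is SAP wording and a one-line calculation, with no new data. Intervals widen by about 25%, and power falls. At a true ICC of 0.01 and usual care at 15%, the difference detectable with 80% power is about 17 points rather than 14 for the pooled contrast. For SCC1 vs SCC2 (SCC2 at 15–30%) it is about 20–22 rather than 17–19. The smaller figures belong to a test running at about 12% error, so part of the apparent loss is not real power. The 3-df check would need about 27 points for the pooled contrast and 29–31 for SCC1 vs SCC2. The Power analysis plans for 4.5 and 7–8 points, so the SAP should state these detectable differences openly.

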Aim 4: Cost-effectiveness analysis. We will track all costs associated with implementing SCC1 and SCC2 beyond those of existing FP services (the costs of which we will also measure), such as labor costs associated with SCC sessions and consults with FP nurses, supervision of the FP nurses (in SCC1), contraceptives and SCM client kits, and cost of intervention materials (posters, SCM instructional videos). Labor costs are based on clinic-specific data, external sources, and our own documentation (e.g., # and length of SCC sessions, FP consults, supervision meetings). Fixed costs will be allocated to the intervention as the fraction of time the premises are used for the intervention (e.g., SCC sessions). Training materials and supplies will be costed at purchase prices. Development costs such as personnel costs for the SCC training workshop will be differentiated from ongoing operational costs, but will exclude research costs (e.g., surveys). We will also evaluate potential efficiencies in operational costs (SCC sessions and ongoing supervision) over time and differentiate between the fixed costs of the intervention and the marginal cost of adding an additional client to inform generalizability to other settings. The analysis will be performed from the clinic perspective as we cannot accurately incorporate costs incurred by the client (e.g., lost earnings on clinic visit days), but the coordinator will track the number and duration of SCC sessions, and the survey will assess transportation and other client costs. We will assess whether the intervention is cost-effective by assessing the cost-effectiveness ratio (CER), defined by the difference in per-capita cost of the two intervention models relative to the control. We will assess average overall and marginal cost per achieved pregnancy (without partner seroconversion) or prevented pregnancy (depending on the patient's desired pregnancy status) and compare those to published values such as Shade et al.⁸⁰ We will estimate confidence intervals for our CERs using bootstrap methods.⁸¹

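### Aim 1 claims each SCC arm beats usual care, but only the pooled contrast and SCC1 vs SCC2 are explicitly defined and powered; state the single-arm contrasts

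*Combined protocol and SAP*

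**What the plan says.** The hypothesis under Aim 1 of the Data Analysis Plan is "Both SCC1 and SCC2 will be superior to usual care, and SCC1 will be superior to SCC2". It has three parts: SCC1 over usual care, SCC2 over usual care, and SCC1 over SCC2.

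The Data analysis paragraph sets the main contrast: "Our primary analysis will be to compare the combined intervention arms (SCC1 & SCC2) against the usual care control". A comparison of the two intervention arms follows. The Power analysis paragraph uses the same pair. It gives a detectable difference of 4.5 points "for our comparison of the usual care arm to the combined SCC1 & SCC2 arms" and 7-8 points for SCC1 against SCC2. It then gives figures for the same two contrasts with contraception and safer-conception methods taken separately. No power is stated for either arm alone against usual care.

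The Aim 1 model sentence compares rates "in the SCC1 and SCC2 interventions compared to the control condition" and will "investigate differences between SCC1 and SCC2 in a separate regression". Aim 2 adopts this by reference: "We will use the same analytic strategy as described for Aim 1". Aim 4 looks at "the difference in per-capita cost of the two intervention models relative to the control".

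**The concern.** A hypothesis should map onto the contrasts that will decide it. Here two of the three parts, each arm against usual care, have no explicitly defined contrast and no stated power. Nothing says which result supports which part.

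The logical gap concerns SCC2. A pooled result better than usual care, together with SCC1 better than SCC2, is compatible with SCC2 having no effect, because SCC1 alone can drive both. The protocol's Arm 2 section presents SCC2 as the lighter option that policy makers could adopt, so SCC2 against usual care is a result the trial needs to report. If the model is left open, the choice between one pooled indicator and two arm indicators could be made after the data are seen.

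**Working it through.** **Inputs.** Usual-care rate 15%, ICC 0.01, 10% attrition and a 2-tailed test (Power analysis); 2 sites per arm and 65 clients per site (Overview). Alpha is not stated; 0.05 two-sided is assumed. Analysed per clinic: 65 × 0.9 = 58.5, taken as 58, so 116 per arm. Design effect = 1 + 57 × 0.01 = 1.57. Effective n = 116 / 1.57 = 73.9 per arm, or 147.8 for the two arms pooled.

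**The plan's own figures first.** Two-proportion test, power = Φ[(d − 1.96·s0)/s1], where s0 is the null and s1 the alternative standard error.

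- Pooled vs usual care at 4.5 points: mean rate (0.15 + 2 × 0.195)/3 = 0.18; s0 = √[0.18 × 0.82 × (1/73.9 + 1/147.8)] = 0.0547; s1 = √[0.1275/73.9 + 0.1570/147.8] = 0.0528. Power = Φ[(0.045 − 0.1073)/0.0528] = Φ(−1.18) = 12%, not over 80%.
- Any single pair at 8 points from 15%: 23%.

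The stated 4.5 and 7-8 points do not reproduce. Ignoring clustering, the pooled figure is still about 13 points.

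**Differences detectable with 80% power.** The text gives 6 sites in the Overview and Study Setting but 9 clinics in Data analysis and Aim 3, so both are shown.

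| Contrast, ICC 0.01 | 6 clinics | 9 clinics |
|---|---|---|
| Pooled vs usual care | 17.1 | about 14 |
| Any single pair | 19.8 | 15.7 |

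Check of 19.8: mean rate 0.249; s0 = √[0.249 × 0.751 × 2/73.9] = 0.0711; s1 = √[(0.1275 + 0.2268)/73.9] = 0.0692; (0.198 − 0.1394)/0.0692 = 0.85, which is 80% power. With 6 clinics, the single-pair figure is 17.6, 23.6 and 27.0 points at ICC 0.005, 0.02 and 0.03 (an assumed range; the plan gives none).

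**Can both planned tests succeed when SCC2 does nothing?** Simulation of 200,000 beta-binomial trials per scenario: 2 clinics of 58 per arm, control 15%, ICC 0.01. Success means z > 1.96 on both planned contrasts.

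| True SCC1 effect (points) | Design effect applied | Standard regression, no correction |
|---|---|---|
| +4.5 | 0.7% | 2.7% |
| +8 | 2.6% | 7.9% |
| +15 | 16% | 31% |
| +20 | 33% | 52% |
| +30 | 70% | 84% |

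On its own contrast with usual care, an inert SCC2 is declared superior in 2.4% of trials (5.9% uncorrected).

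**Precision of a single-arm estimate** (15% in both groups): half-width 1.96 × √[1.57 × 0.15 × 0.85 × (2/116)] = 11.5 points. Pooled: 1.96 × √[1.57 × 0.15 × 0.85 × (1/116 + 1/232)] = 10.0 points.

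**The case against.** The strongest reply is that the single-arm contrasts are probably already intended. The model sentence follows directly on the three-part hypothesis, uses the plural, and agrees with the Overview and Aim 4, which set two models against usual care. A separate regression for SCC1 against SCC2 is also compatible with a first model holding two arm indicators. This stands as a fair reading, and under it the logical gap closes. The primary-analysis paragraph points the other way, however, and the power statement is silent on single arms under either reading.

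A second reply is that the arms are equal in size, so SCC1 against SCC2 already indicates roughly what a single arm against usual care can detect. That is right in principle, but the 7-8 points a reader would borrow is itself wrong.

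Third, the large error rates need an inert SCC2 beside a very effective SCC1. SCC2 shares screening, nurse training, some tools and an added nurse with SCC1, so exactly zero effect is an extreme case. This also stands. The uncorrected column is not the whole plan either, since the plan says of clustering that "we will explore the sensitivity of significance levels using a range of plausible ICCs values".

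A reader might infer that the plan excludes single-arm comparisons, or proposes to declare SCC2 effective from the pooled result. The documents support neither: the wording is ambiguous rather than exclusive, and no section draws that inference. Nor is pooling first a fault; it answers the stated question of what integrating counselling achieves. Rewording the hypothesis to match the pooled contrast would remove the mismatch on paper but leave SCC2's own effect unreported.

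**Conclusion.** The mismatch is real and should be fixed, but its likely harm is modest. Three superiority claims are made, two contrasts are explicitly defined and powered, and the model sentence does not settle whether the arms enter separately. On the pooled reading, SCC2 over usual care cannot be established. With SCC2 inert, both planned tests succeed in about 1-3% of trials at the plan's own effect sizes and about 33% at SCC1 +20 points. On the arm-by-arm reading, what remains is a contrast without stated power, and that power is low: 23% at 8 points, with about 20 points needed for 80%.

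The simulated rates assume 6 clinics, ICC 0.01 and alpha 0.05. With 9 clinics each test has more power, so detectable differences shrink (about 14 and 16 points) and the chance that a strong SCC1 carries both planned tests rises. All the normal-approximation figures are optimistic with two clinics per arm.

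**What to change.** Keep the pooled contrast as primary for the effect of integrating counselling. Then:

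- State that the Aim 1 logistic model, and Aim 2 by reference, has separate SCC1 and SCC2 indicators with usual care as reference.
- Report SCC1 vs usual care, SCC2 vs usual care and SCC1 vs SCC2 as estimates with 95% confidence intervals inflated for clustering, over a stated ICC range that includes 0.01 (for example 0.005 to 0.03, an assumption).
- State that SCC2 efficacy is not inferred from the pooled result.
- Either call the single-arm contrasts secondary estimates without a confirmatory claim, or name a testing order.
- In the Power analysis paragraph, state alpha, add single-arm detectable differences, and correct the 4.5 and 7-8 points. Adding a line to the uncorrected paragraph would not be enough.
- Reconcile the 6-site and 9-clinic counts.

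The data and software are unchanged. The cost is precision and fewer parts of the hypothesis likely to be shown. With 6 clinics and +17 points in both arms, power is about 80% pooled, 69% per arm and 55% for both arms. At +20 for SCC1 and +10 for SCC2, both arm contrasts succeed in 31% of trials and all three parts in about 3%. A cluster-level t test on 3 degrees of freedom, with variance pooled over the arms, gives only 48% pooled and 38% per arm at +17. That is a reason to report estimates and intervals rather than lean on significance.
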